## 6.3. Study Periods

### Screening/Baseline

After participants provide informed consent, they will be assessed for study eligibility. Refer to Section [7.2](#) for detailed eligibility criteria and testing requirements. Screening will include negative test result by RT-PCR. Prior to dosing, a baseline nasopharyngeal swab sample will be collected for retrospective, central laboratory confirmation of SARS-CoV-2 negativity by RT-qPCR.

Participants who are unable to complete screening requirements within the screening period are allowed to be rescreened once, after consultation with the Sponsor.

### Treatment and Efficacy Assessment Period (EAP)

On day 1, participants will be randomized to repeated subcutaneously-administered study drug or placebo as described in Section [8.1](#) and [Figure 1](#). The method of randomization and stratification are described in Section [8.5](#).

Study visits will occur every 4 weeks during the EAP. During these visits, dosing and collection of study information will occur, including an evaluation of any possible signs or symptoms of COVID-19. Signs and symptoms will be evaluated by a clinician (the investigator or designee) as described in Section [9.2.4.2](#), and will be used in the evaluation of the symptomatic SARS-CoV-2 infection (ie, the primary endpoint).

Following the first dose, participants will be monitored for at least 15 minutes and then released from the study site, if medically appropriate. Dosing will continue for the duration of the EAP, with the last visit in the EAP occurring approximately one month after the final dose.

Blood samples will be collected during select EAP visits, for evaluation of drug concentration, immunogenicity, serum antibody concentration, or for exploratory research.

### Follow-up Period

Participants will continue to have visits every 4 weeks during the follow-up period. These visits may occur in person, by phone, or by other means of communication as necessary. These visits will be used to collect safety information and follow up on any COVID-19 signs/symptoms as described in the Schedule of Events. The final study visit will occur (by phone) at 9 months.

## 6.4. Monitoring and Management of Suspected COVID-19

### 6.4.1. Monitoring for Suspected COVID-19

Participants will be monitored for suspected COVID-19 symptoms throughout the study. Participants (or their caregivers, when applicable) will be provided with contact information for the clinical study site and will be given written and verbal instructions to call site personnel as soon as possible if they experience any changes in their health status. This could include any symptoms or signs potentially related to COVID-19 or if they observe any new sense of feeling unwell.

### 6.4.2. Evaluation of Suspected COVID-19

Participants with suspected COVID-19 will undergo an evaluation of symptoms by a study clinician (investigator or designee) as soon as possible (**within 48 hours of symptom onset, if feasible**). To ensure prompt evaluation, an unscheduled visit is highly preferred, unless a scheduled study visit is the soonest visit available.

Signs and symptoms will be evaluated by a clinician (investigator or designee) as described in Section 9.2.4.2, and will be used for the analysis of symptomatic SARS-CoV-2 infection. If the clinician confirms that at least one sign or symptom is related to COVID-19, samples will be collected to perform both **local** and **central** testing for SARS-CoV-2 infection.

Local testing must be performed by RT-PCR using local sample collection and assay standards. A nasopharyngeal (NP) swab sample is the preferred sample type, but other samples (eg, nasal, oropharyngeal, saliva) adhering to local standards are acceptable. An additional NP swab sample will be collected for the purposes of central RT-qPCR testing.

The samples will be collected prior to any administration of post-infection treatment (described below). The qualitative result of the central RT-qPCR will be reported back to the corresponding study site.

### 6.4.3. Laboratory-Confirmed SARS-CoV-2 Infection Obtained Outside of the Study

If a site receives notification from a participant that a positive test result for SARS-CoV-2 infection was obtained outside of the study, the test result will be obtained and documented, and the participant will have an unscheduled study visit as soon as feasible. If the outside documented positive test utilized any assay type other than RT-PCR, the participant will have samples collected to perform local RT-PCR and central RT-qPCR testing for SARS-CoV-2 infection. If the outside test utilized RT-PCR, the participant will only require sample collection for central RT-qPCR testing. In all cases, participants will undergo an evaluation of COVID-19 signs and symptoms by the investigator or designee during the unscheduled visit.

Test results outside of the study will qualify as laboratory-confirmed SARS-CoV-2 infection for the purposes of study analyses, but only if an RT-PCR assay was utilized.

#### **6.4.4. Post-Infection Treatment for Participants with Confirmed Positive SARS-CoV-2 RT-PCR**

Participants with a confirmed positive SARS-CoV-2 RT-PCR at any time during the study (local, central, or documented outside of the study) should be treated with standard of care per local practices and per the investigator's judgment. In addition, casirivimab+imdevimab may be offered to the participant as post-infection treatment if medically appropriate in the investigator's judgment.

If post-infection treatment with casirivimab+imdevimab is deemed medically appropriate, the treatment should be provided through the most expeditious mechanism available. To this end, casirivimab+imdevimab may be given through mechanisms outside of the study in regions where it is approved or authorized. Where regionally approved or authorized, casirivimab+imdevimab should be administered at the approved or authorized dose.

For participants who are able to receive post-infection care at a study site, casirivimab+imdevimab may also be offered to the participant as part of the study. This mechanism can be used, for example, if casirivimab+imdevimab is not regionally approved or authorized for treatment of SARS-CoV-2 infection, or if treatment cannot be made available in an expeditious manner via the approved or authorized mechanisms.

The following investigational dose levels will be offered as part of the study, and may be provided if medically indicated in the investigator's judgement:

- Not hospitalized due to COVID-19 and does not require supplemental oxygen or an increase in baseline oxygen flow rate due to COVID-19: **1200 mg** (600 mg per mAb), administered either intravenously or subcutaneously
- Hospitalized due to COVID-19 and does not require supplemental oxygen due to COVID-19, or requires low-flow supplemental oxygen due to COVID-19: **2400 mg** (1200 mg per mAb), administered intravenously
- Hospitalized due to COVID-19 and requires either high-intensity supplemental oxygen due to COVID-19 or requires mechanical ventilation due to COVID-19: **8000 mg** (4000 mg per mAb), administered intravenously

If feasible, treatment with casirivimab+imdevimab should be provided within 48 hours after a positive RT-PCR result is obtained.

Administration of post-infection treatment with casirivimab+imdevimab will not require unblinding of the participant's randomization assignment (Section 8.7).

#### **6.4.5. Schedule of Events for Participants with Positive SARS-CoV-2 RT-PCR**

Participants with a positive SARS-CoV-2 RT-PCR (from either local or central testing) will discontinue the study drug assigned at randomization and enter the follow-up period. This includes any participant for whom post-infection treatment with casirivimab+imdevimab was offered but was declined by the participant or investigator, or otherwise not received.

All participants with a positive SARS-CoV-2 RT-PCR will have **additional** assessments and sample collections, as noted in the Schedule of Events and summarized below):

- NP swab samples will be collected during unscheduled visits every 7 days ( $\pm 1$  day) for central laboratory RT-qPCR analysis until 2 consecutive negative test results are obtained. During these visits, COVID-19 signs and symptoms will also be evaluated by the investigator or designee.
- Information regarding COVID-19-related medically-attended visits (MAVs; defined in Section 9.2.4.3) will be recorded, and participants will be asked to notify study personnel as soon as possible about such occurrences.

#### **6.4.6. Schedule of Events for Participants with Negative SARS-CoV-2 RT-PCR**

Participants with a negative SARS-CoV-2 RT-PCR will continue to follow the Schedule of Events, and will continue to receive the treatment assigned to them at randomization.

#### **6.4.7. Management of Participants with Positive SARS-CoV-2 Infection at Baseline**

Participants who are negative for SARS-CoV-2 by local RT-PCR at screening but have a positive baseline (day 1) result for SARS-CoV-2 from the central laboratory RT-qPCR will be discontinued from the treatment assigned to them at randomization. These individuals will be eligible for post-infection treatment with casirivimab+imdevimab as defined in Section 6.4.4. However, these participants will not be considered as having received post-infection treatment for the purposes of study analyses.

Individuals who are positive at baseline will not undergo any protocol-defined assessments related to COVID-19 symptom evaluation or SARS-CoV-2 testing, but will directly enter the follow-up period and continue to be followed for safety according to the Schedule of Events.

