### **9.2.1.4. Screening and Baseline Assessments for SARS-CoV-2 Infection**

During the screening period, the investigator or designee will verify that the participant has tested negative for SARS-CoV-2 within the time period specified in Section [7.2.1](#). The screening assessment for SARS-CoV-2 infection will be performed locally using an approved or authorized diagnostic RT-PCR assay, performed according to the study site's standards and procedures.

For local screening test, a nasopharyngeal (NP) swab sample is the preferred sample type, but other samples (eg, nasal, oropharyngeal, saliva) are acceptable if they are collected according to local standards. For tests performed at screening, the local testing result, specimen type, assay type, and date of the test will be recorded in the eCRF.

Baseline SARS-CoV-2 RT-qPCR testing will be performed by a central laboratory NP swab test on day 1. The qualitative results of this baseline central SARS-CoV-2 RT-qPCR will be reported back to the corresponding study site but will not be required prior to study drug administration on day 1.

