3.2. Safety Analysis Set

The safety analysis set (SAF) includes all participants who received any study drug; it is based on the treatment received (as treated). Determination of “as treated” will be based on the actual study drug received. Treatment compliance/administration and all clinical safety variables will be analyzed using the SAF.

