3.3. Pharmacokinetic Analysis Set

The PK analysis set is defined for each study drug separately, includes all participants who received active study drug, and who had at least 1 non-missing result of each respective analyte following the first dose of respective study drug. Participants will be analyzed based on the actual treatment received (as treated) rather than as randomized.

Participants who test positive for SARS-CoV-2 infection during the treatment period and discontinue study drug may be analyzed separately.

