5.9. Analysis of Pharmacokinetic Data

The concentrations of casirivimab and imdevimab in serum over time will be summarized descriptively for each of the treatment groups by age group (subjects ≥ 12 years of age to < 18 years of age, ≥ 40 kg; and subjects ≥ 18 years of age). Associations between covariates that may impact PK of casirivimab and imdevimab and concentrations of the antibodies in serum may be evaluated as appropriate. No formal statistical hypothesis testing will be performed.

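### Protocol 6.4.7 treats baseline-positive participants as not having received post-infection casirivimab+imdevimab in any study analysis, and neither document says where their later safety events and drug concentrations belong

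*Protocol*

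**What the plan says.** Protocol 6.4.7 covers participants who are negative locally at screening but positive on the day 1 central test. They stop the assigned treatment, go directly into follow-up and continue to be followed for safety. "These individuals will be eligible for post-infection treatment with casirivimab+imdevimab as defined in Section 6.4.4". The section then adds that "these participants will not be considered as having received post-infection treatment for the purposes of study analyses".

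Protocol 6.4.4 sets the in-study doses at 1200 mg (IV or SC), 2400 mg (IV) and 8000 mg (IV), according to hospitalisation and oxygen status.

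On the analysis side:

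- **Safety set.** Protocol 11.3.2 and SAP 3.2 define it by treatment received. SAP 3.2 says that the determination "will be based on the actual study drug received". Protocol 11.3.2 promises details in the SAP; SAP 3.2 gives none.
- **Safety periods.** SAP 5.8 summarises events by treatment group over the EAP, follow-up and both combined. The EAP runs by study day, with no break at a post-infection dose.
- **PK set.** SAP 3.3 limits it to recipients of active study drug, grouped as treated. It adds: "Participants who test positive for SARS-CoV-2 infection during the treatment period and discontinue study drug may be analyzed separately". Under SAP 5.9, concentrations "will be summarized descriptively for each of the treatment groups by age group".
- **Efficacy.** The mITT excludes central baseline-positives. SAP 4.5.1 removes efficacy data after the optional 1200 mg dose and after listed anti-SARS-CoV-2 products used for prevention.

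**The concern.** The 6.4.7 sentence reaches every study analysis. The mITT already excludes these participants, so the primary efficacy set does not need it. What it can still affect is the ITT, safety, PK and immunogenicity displays. In safety and PK, calling someone untreated after they have received active drug is at odds with an as-treated definition.

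Safety matters most here. After early closure it is the one domain that the plan commits to summarising; efficacy, PK and immunogenicity are optional. A placebo participant given active drug after day 1 would go on contributing events, with nothing to mark those that followed the active dose. A participant in a 300 mg arm given a further dose could contribute concentrations that do not reflect the 300 mg regimen.

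**Working it through.** No design figure in the plan depends on this point, so the check compares the passages and then bounds the number of people.

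**1. Can a baseline-positive participant be in the safety set?** Yes. Protocol 9.2.1.4 says that the central baseline result "will not be required prior to study drug administration on day 1". Such a participant can receive the day 1 injection, enter the safety set, and then be followed for safety under 6.4.7.

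**2. Does the as-treated wording settle where later events go?** It depends on whether a post-infection dose counts as study drug, which neither document states.

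- If it does not count: Protocol 8.3.2.1 points this way, since it lists receipt of post-infection treatment as a reason to stop study drug. A placebo participant then stays in the placebo column, including events after active drug.
- If it does count: the arms in Protocol 8.1 are 1200 mg then 600 mg Q4W, 300 mg Q4W, 300 mg Q12W, and placebo. None consists of a placebo or 300 mg dose followed by a single 1200, 2400 or 8000 mg dose, so no column is correct.

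Either reading needs a rule.

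**3. Does the PK provision cover the case?** Not clearly. It says that separate analysis may be done, and it concerns people who test positive during the treatment period, a term that neither PK section defines. A day 1 pre-dose sample may or may not fall inside it. A placebo participant enters the SAP PK set only if the post-infection dose counts as active study drug, so the PK question mainly concerns the active arms.

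**4. Do the data-removal rules cover it?** SAP 4.5.1 acts on efficacy only. SAP 4.4.2 restates the post-infection doses with no analysis rule and without the 6.4.7 sentence.

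**5. How many people?** Inputs: 66 enrolled (SAP 1.1), so 66/4 = 16.5 per arm. One participant is 1/17 = 5.9% to 1/16 = 6.3% of an arm. The documents give no baseline-positive rate. Protocol 11.2 allows about 10% for failing either mITT condition, serology included. Taken as a planning ceiling, that is 0.10 × 66 = 6.6 people. For an assumed rate f, the expected number per arm is 16.5f and the chance of at least one in the placebo arm is 1 − (1 − f)^16.5:

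| Assumed f | Expected of 66 | Expected per arm | Chance of ≥1 on placebo |
|---|---|---|---|
| 1% | 0.66 | 0.17 | 15% |
| 2% | 1.32 | 0.33 | 28% |
| 5% | 3.30 | 0.83 | 57% |
| 10% | 6.60 | 1.65 | 82% |

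These count baseline-positives. The number actually given post-infection drug is smaller, because treatment is optional.

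**The case against.** The strongest reply is that 6.4.7 is a labelling rule. It may only separate infection already present at baseline from breakthrough infection, without telling anyone to ignore drug received. The safety and PK sets are as treated, and SAP 5.9 speaks of treatment groups, not assigned regimens. That much stands. A reader might infer that the plan orders these doses into the placebo and assigned-regimen summaries; no passage says so. What the reply does not supply is a rule that places the later data anywhere.

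A second reply is that little PK is exposed. This also stands. As the SAP's copy of the original schedule reads, PK samples fall on days 1, 8, 29, 85, 169 and 225, and ADA samples on days 1, 29 and 169. Someone who goes straight to follow-up would give at most a day 8 sample, if treated before it, and one follow-up sample, with no follow-up ADA sample. The close-out schedule lists neither PK nor ADA.

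A third reply is that the gap is wider than 6.4.7. That is correct: it affects every recipient of post-infection drug. The Amendment 2 optional 1200 mg dose, open to all arms, also has a removal rule for efficacy only. This argues for a broader rule, not for leaving the sentence as it is.

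Finally, SAP Section 1 now designates all endpoints exploratory, and the analyses are descriptive. That lowers the stakes but does not make a mixed placebo column easier to read.

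**Conclusion.** The point holds as an unreconciled conflict with a missing rule. Protocol 6.4.7 is unrestricted, the safety and PK sets are as treated, and nothing assigns events or concentrations that follow casirivimab+imdevimab given outside the assigned regimen. Followed as written, events after active drug may appear under placebo, and a few concentrations after an added dose may appear in the 300 mg summaries.

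The size is small and uncertain. The number is not stated and may be zero; about 7 of 66 is a ceiling that includes serology failures and assumes that everyone accepts treatment. One participant is about 6% of an arm.

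A reader might go further and scale up the 300 mg arm's mean concentration by the ratio of added to assigned dose. The documents do not support that. It would add IV to SC doses as if they were interchangeable, assume dose proportionality and matched sampling times, and ignore continued dosing in the other Q4W participants. The 8000 mg level applies only to participants hospitalised on high-intensity oxygen or mechanical ventilation.

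**What to change.** - **Protocol 6.4.7:** reconcile the sentence with the as-treated definitions in Protocol 11.3.2 and 11.3.3 and with SAP 4.5.1, so that the not-considered rule does not apply to safety or PK. State whether a post-infection dose counts as study drug for the as-treated determination.
- **SAP 3.2 and 5.8:** flag every participant who receives casirivimab+imdevimab outside the assigned regimen, whether baseline-positive or infected later, and show events from that dose onward separately. The same wording can cover the Amendment 2 optional dose.
- **SAP 3.3 and 5.9:** replace the optional separate analysis with a fixed rule: concentrations after such a dose are left out of the regimen summaries and listed. Apply the same rule to any ADA results that exist.

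The cost is one protocol clause, a few lines in the SAP, and a few samples and events moved to separate displays. No dose or clinical rule is altered.

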### **6.5. Study Stopping Rules**

An independent data monitoring committee (IDMC) will actively monitor interim data to review the ongoing safety of participants and may recommend to halt the study or implement changes in the study conduct as deemed necessary. Refer to Section 6.8.1 additional information regarding the IDMC.

### **6.6. End of Study Definition**

The end of study is defined as the date the last participant completes the last study visit, withdraws from the study, or is lost to follow-up (ie, the participant can no longer be contacted by the study site).

### **6.7. Planned Interim Analysis**

Refer to Section 11.5.

## 6.8. Study Committees

### 6.8.1. Independent Data Monitoring Committee

An IDMC will actively review data throughout the study to monitor participant safety and efficacy data. The IDMC can make recommendations about early study closure or changes to the study conduct. The IDMC will also perform planned interim analyses (Section 11.5), and make recommendations based on these analyses. The operation of the IDMC is governed by a charter describing further details, such as procedures (including but not limited to periodic safety monitoring) and requirements for reporting its observations to the Sponsor. The IDMC will conduct periodic data reviews as detailed in the IDMC charter. These data reviews will include all available safety data, including deaths, from all enrolled study participants up to the data cutoff date for the analysis.

### 6.8.2. Safety Monitoring Team

A safety monitoring team at Regeneron may meet periodically to review blinded safety data as needed. The team may be comprised of the medical directors, a Global Patient Safety representative, a Clinical Pharmacology representative and representatives from Biostatistics and Data Management, as well as representatives from Clinical Operations and Regulatory Affairs. The data to be reviewed include, but are not limited to:

- Serious adverse events (SAEs)
- Grade  $\geq 3$  injection-site reactions or grade  $\geq 3$  hypersensitivity reactions
- Treatment-emergent adverse events that result in an early study withdrawal
- Selected laboratory tests, as deemed appropriate by the safety monitoring team

## 7. SELECTION, WITHDRAWAL, AND REPLACEMENT OF PARTICIPANTS

### 7.1. Number of Participants Planned

Approximately 8,752 participants will be enrolled in the study. Additional information on sample size can be found in Section 11.2.

### 7.2. Study Population

Participants enrolled in this study must have an immunocompromised condition, documented evidence of non-response to COVID-19 vaccination, a negative SARS-CoV-2 RT-PCR test result, and must have completed a full standard-of-care course (defined regionally) of COVID-19 vaccination with documented evidence of non-response, unless medically ineligible or contraindicated.

#### 7.2.1. Inclusion Criteria

A participant must meet the following criteria to be eligible for inclusion in the study:

1. Is  $\geq 12$  years of age at randomization

*Note: participants  $<18$  years of age will only be enrolled where permitted by local requirements.*

2. Meets  $\geq 1$  of the following criteria:

- a. Solid organ transplant (SOT) or hematopoietic stem cell transplant (HSCT) recipients receiving immunosuppressive medication
- b. Active hematologic malignancies
- c. Solid organ malignancies receiving active treatment with T cell or B cell immunosuppressive therapy
- d. Primary immunodeficiency (such as hypogammaglobulinemia, common variable immune deficiency, severe combined immunodeficiency)
- e. HIV and CD4  $<200$  cells/microliter
- f. Patients with rheumatologic disease, autoimmune disease, or multiple sclerosis receiving immunosuppressive therapy that modulates Th1, Th17, anti-TNF such as infliximab, adalimumab, etanercept, or B cell responses
- g. Currently receiving any of the following immunosuppressant drugs:
  - T cell suppressing agents (eg,  $\geq 5$  mg prednisone equivalent/day during  $>3$  weeks)
  - Proteasome inhibitors (such as bortezomib, lenalidomide), alemtuzumab, anti-thymocyte globulin, CAR-T therapy, calcineurin inhibitors)
  - Alkylating agents and anthracyclines
  - Antimetabolites and purine analogues, such as mycophenolate, fludarabine, or cladribine
  - B cell targeted therapies, such as rituximab, ocrelizumab, CD19/CD20, and BTK inhibitors
  - mTOR inhibitors

- JAK/STAT pathway inhibitors

3. Has received a full course of standard-of-care COVID-19 vaccination per regional guidance, **or** is deemed medically ineligible or contraindicated to receiving a full course of standard-of-care COVID-19 vaccine
4. Has a documented negative (based on test reference values) serology/antibody response in an anti-SARS-CoV-2 spike (S) protein IgG clinical test (including, but not limited to, RBD-specific tests), **or** ≤50 U/mL on the Elecsys® SARS-CoV-2 S Total Ig test. The test should be performed on a sample collected at least 2 weeks after the final dose of a COVID-19 vaccine and within 3 months prior to randomization

*Note: Lateral flow immunoassay (LFIAs) results will not be accepted. Test should be considered acceptable for clinical use by local standards (approved or with EUA issued by the US FDA or by equivalent local health authority).*
5. Has SARS-CoV-2-negative RT-PCR from a sample collected ≤72 hours prior to randomization, using local assay and sample collection and assay standards

*Note: Historical record of negative result is acceptable, as long as the sample was collected ≤72 hours prior to randomization. Nasopharyngeal swab sample is highly preferred but other sample types (such as nasal, oropharyngeal [OP], or saliva) adhering to local standards are acceptable.*
6. Is willing and able to:
  - a. Provide informed consent signed by study participant or legally acceptable representative
  - b. Comply with clinic visits and study-related procedures, including providing samples for viral load testing
7. Is judged by the investigator to be in stable health based on medical history, physical examination, vital sign measurements, and laboratory measurements performed at screening and/or other times prior to administration of study drug

